5.3.5.12 Hospitalization or Prolonged Hospitalization

Any adverse event that results in hospitalization (i.e., inpatient admission to a hospital) or prolonged hospitalization should be documented and reported as a serious adverse event (per the definition of serious adverse event in Section 5.2.2), except as outlined below.

An event that leads to hospitalization under the following circumstances should not be reported as an adverse event or a serious adverse event:

- Hospitalization for a preexisting condition, provided that all of the following criteria are met:

The hospitalization was planned prior to the study or was scheduled during the study when elective surgery became necessary

The patient has not experienced an adverse event

An event that leads to hospitalization under the following circumstances is not considered to be a serious adverse event, but should be reported as an adverse event instead:

- Hospitalization that was necessary because of patient requirement for outpatient care outside of normal outpatient clinic operating hours

5.3.5.13 Safety Biomarker Data

Adverse event reports will not be derived from exploratory safety biomarker data by the Sponsor, and exploratory safety biomarker data will not be included in the formal safety analyses for this study. In addition, exploratory safety biomarker data will not inform decisions on patient management.

5.4 IMMEDIATE REPORTING REQUIREMENTS FROM INVESTIGATOR TO SPONSOR

Certain events require immediate reporting to allow the Sponsor to take appropriate measures to address potential new risks in a clinical trial. The investigator must report such events to the Sponsor immediately; under no circumstances should reporting take place more than 24 hours after the investigator learns of the event. The following is a list of events that the investigator must report to the Sponsor within 24 hours after learning of the event, regardless of relationship to study drug:

- Serious adverse events (defined in Section 5.2.2; see Section 5.4.2 for details on reporting requirements)
- Adverse events of special interest (defined in Section 5.2.3; see Section 5.4.2 for details on reporting requirements)
- Pregnancies (see Section 5.4.3 for details on reporting requirements)
- Accidental overdoses or medication errors (see Section 5.4.4 for details on reporting requirements)

The investigator must report new significant follow-up information for these events to the Sponsor immediately (i.e., no more than 24 hours after becoming aware of the information). New significant information includes the following:

- New signs or symptoms or a change in the diagnosis
- Significant new diagnostic test results
- Change in causality based on new information
- Change in the event's outcome, including recovery
- Additional narrative information on the clinical course of the event

Investigators must also comply with local requirements for reporting serious adverse events to the local health authority and IRB/EC.

5.4.2 Reporting Requirements for Serious Adverse Events and Adverse Events of Special Interest

5.4.2.1 Events That Occur prior to Study Drug Initiation

After informed consent has been obtained but prior to initiation of study drug, only serious adverse events caused by a protocol-mandated intervention should be reported. The paper Clinical Trial Serious Adverse Event/Adverse Event of Special Interest Reporting Form provided to investigators should be completed and submitted to the Sponsor or its designee immediately (i.e., no more than 24 hours after learning of the event), either by faxing or by scanning and emailing the form using the fax number or email address provided to investigators.

5.4.2.2 Events That Occur after Study Drug Initiation

After initiation of study drug, serious adverse events and adverse events of special interest will be reported until 12 weeks after the final dose of study drug. Investigators should record all case details that can be gathered immediately (i.e., within 24 hours after learning of the event) on the Adverse Event eCRF and submit the report via the electronic data capture (EDC) system. A report will be generated and sent to Safety Risk Management by the EDC system.

In the event that the EDC system is unavailable, the paper Clinical Trial Serious Adverse Event/Adverse Event of Special Interest Reporting Form provided to investigators should be completed and submitted to the Sponsor or its designee immediately (i.e., no more than 24 hours after learning of the event), either by faxing or by scanning and emailing the form using the fax number or email address provided to investigators. Once the EDC system is available, all information will need to be entered and submitted via the EDC system.

Instructions for reporting serious adverse events that occur > 12 weeks after the final dose of study treatment are provided in Section 5.6.

5.4.3 Reporting Requirements for Pregnancies

5.4.3.1 Pregnancies in Female Patients

Female patients of childbearing potential will be instructed to immediately inform the investigator if they become pregnant during the study or within 12 weeks after the final dose of study drug. A paper Clinical Trial Pregnancy Reporting Form should be completed and submitted to the Sponsor or its designee immediately (i.e., no more than 24 hours after learning of the pregnancy), either by faxing or by scanning and emailing the form using the fax number or email address provided to investigators. Pregnancy

should not be recorded on the Adverse Event eCRF. The investigator should discontinue study drug and counsel the patient, discussing the risks of the pregnancy and the possible effects on the fetus. Monitoring of the patient should continue until conclusion of the pregnancy. Any serious adverse events associated with the pregnancy (e.g., an event in the fetus, an event in the mother during or after the pregnancy, or a congenital anomaly/birth defect in the child) should be reported on the Adverse Event eCRF. In addition, the investigator will submit a Clinical Trial Pregnancy Reporting Form when updated information on the course and outcome of the pregnancy becomes available.

5.4.3.2 Pregnancies in Female Partners of Male Patients

Male patients will be instructed through the Informed Consent Form to immediately inform the investigator if their partner becomes pregnant during the study or within 12 weeks after the final dose of study drug. A paper Clinical Trial Pregnancy Reporting Form should be completed and submitted to the Sponsor or its designee immediately (i.e., no more than 24 hours after learning of the pregnancy), either by faxing or by scanning and emailing the form using the fax number or email address provided to investigators. Attempts should be made to collect and report details of the course and outcome of any pregnancy in the partner of a male patient exposed to study drug. When permitted by the site, the pregnant partner would need to sign an Authorization for Use and Disclosure of Pregnancy Health Information to allow for follow-up on her pregnancy. If the authorization has been signed, the investigator should submit a Clinical Trial Pregnancy Reporting Form when updated information on the course and outcome of the pregnancy becomes available. An investigator who is contacted by the male patient or his pregnant partner may provide information on the risks of the pregnancy and the possible effects on the fetus, to support an informed decision in cooperation with the treating physician and/or obstetrician.

5.4.3.3 Congenital Anomalies/Birth Defects and Abortions

Any congenital anomaly/birth defect in a child born to a female patient exposed to study drug or the female partner of a male patient exposed to study drug should be classified as a serious adverse event, recorded on the Adverse Event eCRF, and reported to the Sponsor immediately (i.e., no more than 24 hours after learning of the event; see Section [5.4.2](#)).

A spontaneous abortion should be classified as a serious adverse event (as the Sponsor considers abortions to be medically significant), recorded on the Adverse Event eCRF, and reported to the Sponsor immediately (i.e., no more than 24 hours after learning of the event; see Section [5.4.2](#)).

If a therapeutic or elective abortion was performed because of an underlying maternal or embryofetal toxicity, the toxicity should be classified as a serious adverse event, recorded on the Adverse Event eCRF, and reported to the Sponsor immediately (i.e., no more than 24 hours after learning of the event; see Section [5.4.2](#)). A therapeutic or

elective abortion performed for reasons other than an underlying maternal or embryofetal toxicity is not considered an adverse event.

All abortions should be reported as pregnancy outcomes on the paper Clinical Trial Pregnancy Reporting Form.

5.4.4 Reporting Requirements for Cases of Accidental Overdose or Medication Error

Accidental overdose and medication error (hereafter collectively referred to as "special situations"), are defined as follows:

- Accidental overdose: accidental administration of a drug in a quantity that is higher than the assigned dose
- Medication error: accidental deviation in the administration of a drug

In some cases, a medication error may be intercepted prior to administration of the drug.

Special situations are not in themselves adverse events, but may result in adverse events. Each adverse event associated with a special situation should be recorded separately on the Adverse Event eCRF. If the associated adverse event fulfills seriousness criteria, the event should be reported to the Sponsor immediately (i.e., no more than 24 hours after learning of the event; see Section [5.4.2](#)). For MTT1041A or placebo, adverse events associated with special situations should be recorded as described below for each situation:

- Accidental overdose: Enter the adverse event term. Check the "Accidental overdose" and "Medication error" boxes.
- Medication error that does not qualify as an overdose: Enter the adverse event term. Check the "Medication error" box.
- Medication error that qualifies as an overdose: Enter the adverse event term. Check the "Accidental overdose" and "Medication error" boxes.

In addition, all special situations associated with MTT1041A or placebo, regardless of whether they result in an adverse event, should be recorded on the Adverse Event eCRF and reported to the Sponsor immediately (i.e., no more than 24 hours after learning of the event). Special situations should be recorded as described below:

- Accidental overdose: Enter the drug name and "accidental overdose" as the event term. Check the "Accidental overdose" and "Medication error" boxes.
- Medication error that does not qualify as an overdose: Enter the name of the drug administered and a description of the error (e.g., wrong dose administered, wrong dosing schedule, incorrect route of administration, wrong drug, expired drug administered) as the event term. Check the "Medication error" box.

- Medication error that qualifies as an overdose: Enter the drug name and "accidental overdose" as the event term. Check the "Accidental overdose" and "Medication error" boxes. Enter a description of the error in the additional case details.
- Intercepted medication error: Enter the drug name and "intercepted medication error" as the event term. Check the "Medication error" box. Enter a description of the error in the additional case details.

As an example, an accidental overdose that resulted in a headache would require two entries on the Adverse Event eCRF, one entry to report the accidental overdose and one entry to report the headache. The "Accidental overdose" and "Medication error" boxes would need to be checked for both entries.

5.5 FOLLOW-UP OF PATIENTS AFTER ADVERSE EVENTS

5.5.1 Investigator Follow-Up

The investigator should follow each adverse event until the event has resolved to baseline grade or better, the event is assessed as stable by the investigator, the patient is lost to follow-up, or the patient withdraws consent. Every effort should be made to follow all serious adverse events considered to be related to study drug or trial-related procedures until a final outcome can be reported.

During the study period, resolution of adverse events (with dates) should be documented on the Adverse Event eCRF and in the patient's medical record to facilitate source data verification.

All pregnancies reported during the study should be followed until pregnancy outcome.

5.5.2 Sponsor Follow-Up

For serious adverse events, adverse events of special interest, and pregnancies, the Sponsor or a designee may follow up by telephone, fax, email, and/or a monitoring visit to obtain additional case details and outcome information (e.g., from hospital discharge summaries, consultant reports, autopsy reports) in order to perform an independent medical assessment of the reported case.

5.6 ADVERSE EVENTS THAT OCCUR AFTER THE ADVERSE EVENT REPORTING PERIOD

The Sponsor should be notified if the investigator becomes aware of any serious adverse event that occurs after the end of the adverse event reporting period (defined as 12 weeks after the final dose of study drug), if the event is believed to be related to prior study drug treatment. These events should be reported through use of the Adverse Event eCRF. However, if the EDC system is not available, the investigator should report these events directly to the Sponsor or its designee, either by faxing or by scanning and emailing the paper Clinical Trial Serious Adverse Event/Adverse Event of Special Interest Reporting Form using the fax number or email address provided to investigators.

5.7 EXPEDITED REPORTING TO HEALTH AUTHORITIES, INVESTIGATORS, INSTITUTIONAL REVIEW BOARDS, AND ETHICS COMMITTEES

The Sponsor will promptly evaluate all serious adverse events and adverse events of special interest against cumulative product experience to identify and expeditiously communicate possible new safety findings to investigators, IRBs, ECs, and applicable health authorities based on applicable legislation.

To determine reporting requirements for single adverse event cases, the Sponsor will assess the expectedness of these events using the following reference document:

- MSTT1041A Investigator's Brochure

The Sponsor will compare the severity of each event and the cumulative event frequency reported for the study with the severity and frequency reported in the applicable reference document.

Reporting requirements will also be based on the investigator's assessment of causality and seriousness, with allowance for upgrading by the Sponsor as needed.

6. STATISTICAL CONSIDERATIONS AND ANALYSIS PLAN

The analysis of the data from the double-blind treatment period will be performed when all patients have either completed the end of the treatment visit (Week 16) or discontinued early from the study.

The analysis of complete data for the study, including data from the double-blind treatment period and 8-week safety follow-up period, will be performed when all patients have either completed the double-blind treatment period and 8-week safety follow-up period or discontinued early from the study, all data from the study are in the database, and the database is locked.

Personnel who perform the blinded-efficacy assessments will remain blinded to individual treatment assignment until after the study is completed (after all patients have either completed the double-blind treatment period and 8-week safety follow-up period or discontinued early from the study), all data from the study are in the database, and the database is locked.

6.1 DETERMINATION OF SAMPLE SIZE

Approximately 90 patients in total will be randomized in a 1:1 ratio to 490 mg SC MSTT1041A or placebo Q4W. The sample size provides at least 80% power to detect a difference of 34% in the percent change from baseline in EASI score at Week 16 between MSTT1041A- and placebo-treated patients, assuming a standard deviation of 40.6 for placebo-treated patients. The same number of patients can also provide at least 80% power to detect 1) a difference of 27% between MSTT1041A- and

placebo-treated patients in the proportion of patients achieving IGA scores of 0 or 1 at Week 16, assuming the percentage is 2% in placebo-treated patients, respectively, 2) a difference of 32% between MSTT1041A- and placebo-treated patients in the proportion of patients achieving EASI-75 at Week 16, assuming the percentage is 13% in placebo-treated patients, and 3) a difference of 30% between MSTT1041A- and placebo-treated patients in percent change from baseline to Week 16 in pruritus NRS, assuming a standard deviation of 37.3 for placebo-treated patients. The sample size is calculated at a two-sided significance level of 0.05 and assumes 25% dropout.

6.2 SUMMARIES OF CONDUCT OF STUDY

The number of patients who enroll, discontinue, or complete the study will be summarized. Reasons for treatment discontinuation and premature study withdrawal, as well as treatment failure, will be listed and summarized. Enrollment and major protocol deviations will be listed and evaluated for their potential effects on the interpretation of study results. Exposure to study treatment (number of study drug treatments and duration of treatment) will be summarized. All summaries will be presented according to randomized treatment assignment.

6.3 SUMMARIES OF TREATMENT GROUP COMPARABILITY

Demographic and baseline characteristics (including age, sex, race/ethnicity, concomitant AD medication use, and comorbid illnesses) will be summarized using means, standard deviations, medians, and ranges for continuous variables and proportions for categorical variables, as appropriate. Summaries will be presented overall and by treatment group.

6.4 EFFICACY ANALYSES

Efficacy analyses will be based on the intent-to-treat (ITT) approach. All patients randomized (ITT population) will be included in the analysis, with patients grouped according to the treatment assigned at randomization. Hypothesis testing for the efficacy endpoints will be performed for each MSTT1041A dose level and the placebo group.

6.4.1 Primary Efficacy Endpoint

The primary efficacy endpoint for this study is percent change from baseline to Week 16 of total EASI score. A mixed-effect model for repeated measures (MMRM) model will be used, with percent change (post baseline change divided by baseline value) as the dependent variable. The model will include baseline value of the EASI score, treatment arms, visits, treatment arm by visit interaction, and stratification factors as listed in Section 3.1. To account for repeated observations with patients, a random patient effect will be added to the model. The MMRM model will provide adjusted least-square means of percent change from baseline at Week 16 for each of the treatment arms with the corresponding standard error, 95% CI and p-values.

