Approximately 90 patients will be randomized in a 1:1 ratio to receive MSTT1041A 490 mg SC or placebo SC every 4 weeks (Q4W). Randomization will be stratified by baseline disease severity IGA score (IGA=3 vs. IGA=4) and region. Patients will be given a loading dose of 245 mg SC MSTT1041A or placebo at the Week 1 visit to reduce the time required to achieve steady-state exposure of MSTT1041A (see Section 4.3.2.1 for details).

During the double-blind treatment and follow-up period, laboratory tests and clinical assessments will be performed at the site (office visits). Additionally, telephone visits will be conducted to assess changes in health status, concomitant medications, and sleep and pruritus NRS score.

[Figure 1](#) presents an overview of the study design. A schedule of activities is provided in [Appendix 1](#).

Figure 1 Study Schema

D=day; Q4W=every 4 week; Wk=week.

^a Additional loading dose on Week 1 of 245 mg MSTT1041A (or placebo) SC.

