6.4.2 Secondary Efficacy Endpoints

All secondary endpoints involving binary outcome measures will be analyzed using the Cochran-Mantel-Haenszel chi-square test. Patients with missing results at Week 16 will be considered non-responders for the corresponding endpoint.

Percent and absolute change from baseline for (approximately) continuous endpoints will be analyzed using a MMRM model as described for primary endpoint in Section 6.4.1. The MMRM model will provide adjusted least-square means of percent change from baseline at Week 16 for each of the treatment arms with the corresponding standard error, 95% CI and p-values.

Summary statistics of the (approximately) continuous endpoints will be calculated for each treatment arm in absolute changes and raw values. Mean, standard deviations, medians, and lower and upper quartiles, as well as minimum and maximum will be reported. For all summaries involving change from baseline, patients without baseline values will be excluded from the analyses.

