6.9 SENSITIVITY ANALYSIS

Sensitivity analyses will be performed to evaluate the robustness of primary and secondary analyses. The details of the sensitivity analyses will be specified in the Data Analysis Plan.

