Appendix 1: Schedule of Activities

- ^a If a patient is unable to complete all study visits and assessments, the patient should be asked to return to the clinic for an early termination visit. This visit should occur approximately 4 weeks after the final dose of study drug (see Section 4.6.2).
- ^b Any of the study procedures noted may be performed at an unscheduled visit, but not all are required.
- ^c Informed consent must be documented before any study-specific screening procedure is performed.
- ^d Includes evaluation of the head, eyes, ears, nose, and throat, and the cardiovascular, dermatologic, musculoskeletal, respiratory, gastrointestinal, and neurologic systems. Record abnormalities observed at baseline on the General Medical History and Baseline Conditions eCRF. At subsequent visits, record new or worsened clinically significant abnormalities on the Adverse Event eCRF.
- ^e Perform a limited, symptom-directed examination at specified timepoints and as clinically indicated. Record new or worsened clinically significant abnormalities on the Adverse Event eCRF.
- ^f Questionnaires (██████████, pruritus and sleep NRS) will be self- or interviewer-administered before the patient receives any information on disease status, prior to the performance of non-PRO assessments, and prior to the administration of study treatment.
- ^g Assessment will be conducted only during an office visit (i.e., not at a telephone visit).
- ^h Will only be conducted at a telephone visit. For the Week 2 visit, if the patient does not have an office visit (chooses a telephone visit), collect pruritus and sleep NRS.
- ⁱ Includes respiratory rate, pulse rate, and systolic and diastolic blood pressure, ideally while the patient is in a seated position, and temperature. Record abnormalities observed at baseline on the appropriate eCRF. At subsequent visits, record new or worsened clinically significant abnormalities on the Adverse Event eCRF.
- ^j All women of childbearing potential will have a serum pregnancy test at screening. Urine pregnancy tests will be performed at specified subsequent visits. If a urine pregnancy test result is positive, it must be reported immediately, and study drug will not be administered that day. The positive urine pregnancy result must be confirmed by a serum pregnancy test. Refer to Section 5.4.3.1 for management of a patient with a positive pregnancy test.

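### Section 6.4.1 handles within-patient correlation by a random patient effect alone and names no residual covariance, so the validity of the Week 16 standard error rests on assumptions the plan does not support

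*Combined protocol and SAP*

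**What the plan says.** Section 6.4.1 calls the primary analysis an MMRM. Its fixed effects are baseline EASI, arm, visit, arm by visit and the stratification factors. Its one provision for within-patient dependence is: "To account for repeated observations with patients, a random patient effect will be added to the model". The Primary Analysis text of the synopsis repeats that sentence. Section 6.4.2 carries the model over to the continuous secondary measures, whose "endpoints will be analyzed using a MMRM model as described for primary endpoint in Section 6.4.1".

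No section names a residual covariance, a fallback structure or a degrees-of-freedom method. Section 6.9 refers to a later document, but only for sensitivity analyses: "The details of the sensitivity analyses will be specified in the Data Analysis Plan".

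The visits in the model are not listed either. The EASI row of Appendix 1 marks Weeks 1, 2 (office visits only), 4, 8, 12, 16 and 24, plus early termination and unscheduled visits; Week 20 is a phone visit without EASI. Section 6 describes a separate analysis at the end of treatment ("The analysis of the data from the double-blind treatment period will be performed when all patients have either completed" Week 16 or left early), which suggests that the model stops at Week 16, but Section 6.4.1 does not say so.

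The only EASI variability figure is in Section 6.1: "assuming a standard deviation of 40.6 for placebo-treated patients", at Week 16.

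**The concern.** A random patient effect with independent, equal-variance residuals imposes one variance at every visit and one correlation between every pair of visits. The primary comparison concerns a single visit, Week 16. If the spread of percent change differs between early visits and Week 16, or if correlation weakens as visits lie further apart, the model's standard error for that visit can be wrong. The confidence interval and p-value of the primary test go wrong with it, and the continuous secondary endpoints inherit the problem.

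The choice is also left open. Two statisticians could follow Section 6.4.1 faithfully, one with compound symmetry and one with an unstructured matrix, and report different primary p-values. That should be settled before unblinding.

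**Working it through.** **1. The plan's own figure.** Inputs from Section 6.1: about 90 patients 1:1, difference 34, SD 40.6, two-sided 0.05, 25% dropout. The SD is stated for placebo; I assume it for both arms. Evaluable per arm: 45 × 0.75 = 33.75. With 34 per arm, SE = 40.6 × √(2/34) = 9.85, and 34/9.85 = 3.45. A two-sample t-test has 92.5% power (91.8% with 33 per arm). The claim of at least 80% holds. This is a plain Week 16 comparison, so it does not depend on the repeated-measures covariance.

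**2. What the random patient effect implies.** With patient variance τ² and residual variance σ², every visit has variance τ² + σ² and every pair of visits has correlation τ²/(τ² + σ²). That is compound symmetry, with 2 parameters.

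**3. Complete data.** With separate arm-by-visit means, the fitted variance is the mean of the visit variances. Hence

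- R = reported SE / true SE = √(mean visit variance) / (Week 16 SD)
- true size of the nominal 5% test = 2Φ(−1.96 R)

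Example, SDs 30, 38, 43, 43, 42, 40.6 at Weeks 1, 2, 4, 8, 12, 16: the squares sum to 9454.36, mean 1575.73, root 39.70. R = 39.70/40.6 = 0.978 and size = 2Φ(−1.917) = 5.5%.

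Every SD before Week 16 below is assumed. Ranges run between change linear in log-week and change linear in week.

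| Assumed SD profile, ending at 40.6 | R | Two-sided size |
|---|---|---|
| Flat | 1.000 | 5.0% |
| 38 at Week 1, rising | 0.963–0.972 | 5.7–5.9% |
| 35 at Week 1, rising | 0.920–0.941 | 6.5–7.1% |
| 20 at Week 1, rising | 0.725–0.800 | 11.7–15.5% |
| 30, 38, 43, 43, 42, 40.6 | 0.978 | 5.5% |
| 45 at Week 1, falling | 1.048–1.065 | 3.7–4.0% |
| 50 at Week 1, falling | 1.104–1.139 | 2.6–3.1% |

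**4. With dropout.** Simulation: 1500 null trials per profile, 45 per arm, 25% completely random dropout, half of Week 2 EASI missing, correlation 0.95 per week apart (the missingness pattern and correlation are assumed). The model had baseline EASI, IGA stratum and a two-level region, fitted by REML with Kenward-Roger tests. Rising and falling SDs were linear in visit order. Rescue handling was not modelled. Monte Carlo 95% error is about 1.1 points near 5% and 1.8 near 15%.

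| Profile | Size, random patient effect | Size, unstructured | Random patient effect: mean reported SE vs actual |
|---|---|---|---|
| Flat | 5.3% | 4.2% | not tabulated |
| 35 rising | 7.1% | 4.3% | 8.6 vs 9.5 |
| 20 rising | 14.8% | 4.3% | 7.0 vs 9.4 |
| 30, 38, 43, 43, 42, 40.6 | 6.0% | 4.1% | not tabulated |
| 50 falling | 3.3% | 4.2% | 10.4 vs 9.8 |

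The unstructured model reported 9.5 against an actual 9.4–9.6 in every profile.

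**5. Equal variances with dropout.** With flat SDs and correlation that decays over time, random-intercept fits without the Kenward-Roger adjustment gave a mean SE of 9.08 against an actual 9.58 (size about 6.3%, 2000 runs, error about 1 point). Under a different assumed correlation they gave 9.18 against 9.88 (about 7%, 400 runs, error about 2.5 points). The model treats an early score as just as informative about a missing Week 16 value as a late one. The effect is modest, and the Kenward-Roger figure of 5.3% is compatible with 5%, but equal variances alone do not guarantee a correct SE.

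**The case against.** The best defence is that Section 6.4.1 says MMRM, a label often used for an unstructured within-patient covariance, and nowhere states independent, equal-variance residuals. On that view the document leaves something out but specifies nothing wrong. Part of this stands: the sponsor may intend an unstructured matrix. But a random patient effect on top of one would be redundant and not separately identifiable, so the sentence as written fits a random-intercept model more naturally. The later plan in Section 6.9 would be a natural place for the detail, yet only sensitivity analyses are deferred to it.

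A second defence is that every size other than the flat 5.0% comes from invented SDs. That is correct. Among the rising and non-monotone profiles shown, only the one in which the SD doubles from 20 to 40.6 exceeds 7.1%. A reader might infer that the primary test is known to be liberal, at 12–15%. The documents do not support that: they give no SD before Week 16, and a falling profile makes the test conservative.

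Third, this is a Phase II trial with about 92% power for its primary difference and no contradictory passages. That bears on how serious the point is; it does not supply the missing covariance.

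**Conclusion.** The point holds as a weakness in how the primary model is specified. Under the usual fit of the sentence in Section 6.4.1, a correct Week 16 standard error requires, with complete data, that the Week 16 variance be close to the average over visits. With the planned dropout it also leans on a constant correlation. The documents give no basis for either condition. Direction and size are unknown: the test may be liberal, correct or conservative, and all the size figures above are hypothetical.

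Two further inferences should be resisted. One is that the trial is underpowered: the stated power is reproduced and does not depend on this model. The other is that equal visit variances would make the standard error safe: that is true for complete data only.

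The plan should be changed before unblinding because a better method costs little. Confidence is medium, since the sponsor's intended residual structure is not stated.

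**What to change.** In Section 6.4.1 and the synopsis, replace the random-patient-effect sentence with wording such as: *Within-patient correlation will be modelled by an unstructured covariance over the scheduled post-baseline EASI visits through Week 16 (Weeks 1, 2 when done in the office, 4, 8, 12 and 16), with Kenward-Roger degrees of freedom.*

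Pre-specify a fallback for non-convergence that keeps visit-specific variances and suits unequally spaced visits, for example heterogeneous first-order ante-dependence. If a simpler structure with a sandwich standard error is the last resort, state its small-sample correction and degrees of freedom. A sandwich estimator repairs only the standard error: if dropout depends on earlier scores, a wrong covariance can also bias the Week 16 estimate.

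Cost: up to 6 × 7/2 = 21 covariance parameters instead of 2 (15 if Week 2 is left out), and possibly a larger reported standard error. In the simulation 20 of 7500 unstructured fits (0.3%) missed a strict convergence criterion, so the fallback is worth writing down.

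As a separate clarification, Section 6.4.2 should say which pruritus NRS visits enter its model. Phone scores at Weeks 6, 10 and 14 could bring the total to nine visits, or 9 × 10/2 = 45 parameters.
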